8.3.2. Baseline characteristics

The number of participants screened and enrolled or excluded will be summarized according to reason for exclusion. Of the enrollees, the number of patients discontinued or lost to follow-up will be recorded by reason and time of discontinuation. These figures will be summarized in a CONSORT flow diagram.

Subjects in each treatment group will be described according to baseline characteristics. The description will be in terms of medians and interquartile ranges for continuous variables and using counts and percentages for categorical variables. Standard statistical tests of significance of imbalance in baseline characteristics will be performed.

8.3.3. Primary analysis

The primary hypothesis for non-inferior efficacy will be assessed by calculating the two-sided 95% confidence interval (CI) for the difference in proportions of cured subjects. The CI will be calculated using Wilson's score method.

Interpretation of the CI will be as follows:

- if the two-sided 95% CI for the difference in cure rates (AM schedule PZQ schedule) lies entirely above -10% then non-inferiority of the AM schedule is concluded;
- if the 95% CI for the difference in cure rates includes -10%, then non-inferiority cannot be established;
- if the 95% CI for the difference in cure rates lies entirely below -10%, then the AM regimen is clinically inferior to the standard regimen.

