4.3. Sample size

The sample size was calculated on the parasitological cure rate endpoint after the first course of AM, to test the hypothesis that AM is non-inferior to PZQ: at least a 65% cure rate with AM as compared to a 75% cure rate with PZQ according to the following rationale. We consider that a cure rate (CR) of 65% is clinically acceptable as threshold for non-inferiority for the AM combination, for the following reasons: a cure rate above 65% would be very satisfactory compared to all alternative drugs evaluated so far against schistosomiasis, and an efficacy slightly lower than that of PZQ would be largely compensated by the positive clinical effect due to concomitant malaria suppression. Note that this is likely to be marginal in North Senegal where malaria transmission is low, but this "dual" effect could be a major added-value in many other co-endemic regions with higher malaria transmission

Sample size was calculated by simulation to obtain 80% power. The required sample size is 300 schoolchildren per arm. To account for a 20% loss to follow up, the total number of children to be recruited will be 726 (363 per arm). With the same sample size, superiority of repeated courses of AM to PZQ (cure rate of at least 85% after 3 courses) can also be demonstrated with a similar power (i.e. secondary endpoint).

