5.4. Laboratory procedures

5.4.1. Field tests

Microscopy

Parasitological examination of urine and stool by microscopy will be applied for the detection of *Sh* and *Sm* eggs to assess the primary endpoint (treatment efficacy), since it remains the WHO-established standard for diagnosis of schistosomiasis and assessment of treatment response. For each participant, two urine and two stool samples will be collected at two different days. Per feces sample, two Kato-Katz slides of 25 mg fecal material will be prepared and microscopically examined for *S. mansoni* eggs; each urine sample will be analyzed by the standard filtration technique for the detection of *S. haematobium* eggs. *Sm* and *Sh* infection intensity (average number of eggs per 25 mg gram of stool and per 10 ml of urine respectively) will be determined to determine the intensity of the infection according to WHO criteria ⁷⁴. Microscopy will be performed in the laboratory of the Public Health

facility in Richard Toll by experienced lab technicians, after specific training from an ITM expert. Other intestinal parasites detected by the two methods will also be recorded. For quality control, a random representative number of the slides read per day will be re-read by a second microscopist and the results will be compared for quality control. In case of discordant results, a third observation will be required to validate the result.

POC-CCA

A lateral flow immunochromatographic point-of-care assay (POC-CCA) will be used for the detection of *Schistosoma* circulating cathodic antigens in urine. The commercially available rapid immunochromatographic dipstick will be used (Rapid Medical Diagnostics, Pretoria, South Africa) and tests will be performed according to the manufacturer instructions. Briefly, 2 drops of urine will be transferred into the cassette and the results will be read after 20 minutes. The results will be categorized as negative or positive (trace CCA results will be considered positive) and for the positive, based on the intensity of the band, a concentration of the sample will be estimated in ng/ml (data unpublished), as a semi-quantitative measure of intensity of infection.

Urine reagent strip test

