8.3.4. Secondary and tertiary analysis

Secondary analyses

The efficacy of the two treatments over time will be assessed both by calculating the two-sided 95% CI for the difference in proportions of cured subjects at different time points as well as using a mixed effects logistic regression model. Schistosomiasis infection at specific time points will be used as the outcome and treatment and visit as independent variables with a random intercept. Subsequent analyses of the cure rate per *Schistosoma* species and by *Schistosoma* infection intensity will be analyzed in a similar way including those characteristics as covariates in the model. The analyses for

ERR will be done using a linear mixed effects model with a random intercept and a logit link function separately for each *Schistosoma species*. All comparison of proportions will be done using the Chi-square or Fisher's exact test and comparison of continuous characteristics will be done using the Wilcoxon rank sum test. The sensitivity of a specific diagnostic test will be calculated as the proportion of children with schistosomiasis (based on the reference standard used) who have a positive result. The specificity of a diagnostic test will be calculated as the proportion of children without schistosomiasis who have a negative result. The positive predictive value of a diagnostic test will be calculated as the proportion of children with schistosomiasis with a positive result. The negative predictive value of a diagnostic test will be calculated as the proportion of people with a negative result who do not have schistosomiasis. These different values of both novel and classic diagnostic tests will be calculated together with 95% confidence intervals. Composite reference standards will be created by the investigators of the study and will be used as a comparison. An alternative reference standard will be calculated using latent class analysis methodology. The prevalence and patterns of resistant mutations between the two treatment groups will be compared using Chi-square or Fisher's exact test.

Safety analyses

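### The primary non-inferiority interval makes no use of the baseline egg counts that every child has, so the week-4 decision gives up some precision at no saving

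*Protocol*

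**What the plan says.** Section 8.3.3 (Primary analysis) tests non-inferiority by "calculating the two-sided 95% confidence interval (CI) for the difference in proportions of cured subjects". It names the interval: "The CI will be calculated using Wilson's score method". If the interval "lies entirely above -10% then non-inferiority of the AM schedule is concluded"; two further rules cover an interval that includes -10% and one that lies wholly below it. No covariate or stratum enters.

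The baseline information is already in the plan. Section 4.2 requires eggs in urine or stool for entry. Section 5.1 schedules microscopy at recruitment, before dosing. Section 5.4.1 quantifies "infection intensity (average number of eggs per 25 mg gram of stool and per 10 ml of urine respectively") for Sm and Sh. Section 8.2 uses the baseline count as the denominator of the egg reduction rate.

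Intensity is also treated as relevant to cure. Secondary objective 3 (section 2.2) looks at cure by initial intensity, and section 8.3.4 analyses cure by species and intensity by "including those characteristics as covariates in the model". That model is secondary. Randomisation is stratified by species (section 4.4), and the primary interval does not use that either.

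**The concern.** The primary outcome is absence of eggs on microscopy at week 4, and the baseline egg count is the same measurement taken before treatment. If heavier infections are less likely to be egg-negative at week 4, part of the child-to-child variation in cure can be predicted from data in hand. A crude difference leaves that variation in the standard error, so the interval that decides the trial is wider than it needs to be.

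This matters because the design has little to spare: it is sized for 80% power, and the crude formula needs almost all of the 300 per arm. A modest gain in precision at no data cost is worth having when the decision turns on whether one confidence limit clears -10%.

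**Working it through.** **Inputs.** Margin 10 points and a two-sided 95% interval, that is one-sided 0.025 (8.3.3). Section 4.3 gives "at least a 65% cure rate with AM as compared to a 75% cure rate with PZQ", 300 per arm, and "Sample size was calculated by simulation to obtain 80% power". Equal true cure of 75% in both arms is inferred: 4.3 presents 65% as the threshold for AM, and if it were the true AM rate, the true difference would sit on the margin and power would be only the one-sided error of 2.5%. The share of variance in cure explained by baseline intensity (R² = ρ²) is not given anywhere and is varied.

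**Reproducing the plan's figure.** n per arm = 2 × 0.75 × 0.25 × (1.96 + 0.8416)² / 0.10² = 0.375 × 7.849 / 0.01 = 294.3, so 295 against 300 stated. The inferred inputs and the crude method reproduce the design, which therefore contains no allowance for adjustment.

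**Unadjusted power at 300 per arm.** SE = √(2 × 0.1875 / 300) = 0.03536. Then 0.10 / 0.03536 = 2.828, and Φ(2.828 − 1.96) = Φ(0.868) = 80.7%.

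**Adjusted power.** Adjustment on the risk-difference scale multiplies the variance by about 1 − ρ², so power = Φ(2.828 / √(1 − ρ²) − 1.96).

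| ρ | R² | Power | Gain (points) |
|---|---|---|---|
| 0 | 0 | 80.7% | 0 |
| 0.1 | 0.01 | 81.1% | 0.4 |
| 0.2 | 0.04 | 82.3% | 1.6 |
| 0.3 | 0.09 | 84.3% | 3.5 |
| 0.4 | 0.16 | 87.0% | 6.3 |

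On the R² scale, power is 81.5% at 0.02, 82.7% at 0.05, 84.6% at 0.10 and 86.6% at 0.15. The number per arm needed for 80% power falls from 295 to 289 at R² 0.02 and to 251 at R² 0.15, that is 6 to 44 fewer. The 95% half-width falls from 6.93 points (R² 0) to 6.75 (0.05), 6.57 (0.10) and 6.39 (0.15).

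**Simulation check.** There were 4,000 trials per setting at 300 per arm. The crude score interval was compared with a risk difference standardised from a logistic model, with an influence-function standard error.

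| R² | Crude power | Adjusted power |
|---|---|---|
| 0 | 81.1% | 80.8% |
| 0.016 | 81.0% | 81.6% |
| 0.044 | 80.7% | 81.2% |
| 0.081 | 80.8% | 84.0% |
| 0.147 | 81.1% | 87.4% |

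Monte Carlo error is about 0.6 points per entry (√(0.81 × 0.19 / 4000)). With the true difference at -10 points, one-sided error was 0.023 to 0.029 for the crude interval and 0.022 to 0.027 for the adjusted one. The simulation used one standardised log count, not the two species-specific counts proposed below, so it supports the direction and the validity more firmly than the exact gain.

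**The case against.** The strongest reply is that nothing here is wrong. A score interval for a difference in proportions, read against a stated margin, is a standard and transparent non-inferiority analysis. It keeps its type I error, and the sample size was built on it. That stands: this is a question of efficiency.

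The size is also open to challenge. The protocol gives no intensity-cure association, and section 1.1.2 notes that egg output varies strongly, which would weaken any correlation. At ρ of 0.1 to 0.2 the gain is under 2 points. Children infected with one species sit at or near zero on the other count, and cure requires both species to be negative, so the one-count simulation does not settle the gain for the proposed model. These points stand too, and they are why the result is given as a range that starts near zero.

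A reader might infer two stronger claims. One is that the crude analysis is biased because a chance imbalance in intensity goes uncorrected. The documents do not support this: under randomisation the interval already allows for chance imbalance. The other is a gain of around 10 points. That needs a correlation of about 0.5 (power 90.4%), which would be strong prediction of a binary outcome by egg counts, and nothing in the protocol supports assuming it.

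It can also be said that the plan already adjusts. The secondary models in 8.3.4 include intensity, and the synopsis lists a mixed effects logistic model next to the interval for the primary hypothesis. But 8.3.4 defines that model by treatment and visit with a random intercept, intensity is added only in the secondary analyses, and the decision rule in 8.3.3 reads the crude interval alone. Those analyses do not change what decides the trial.

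**Conclusion.** The point holds as a cheap improvement, not as the correction of an error. Section 8.3.3 decides non-inferiority without a baseline measurement that is scheduled for every child and that the plan itself links to cure. The cost is precision: about 0 to 6 points of power at 300 per arm, for a correlation of 0 to 0.4 between baseline intensity and cure.

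This rests on 75% true cure in both arms, inferred but consistent with the stated sample size, and on an association that the protocol does not report. If intensity does not predict cure, adjustment gains nothing and loses essentially nothing (80.8% against 81.1% in simulation, within Monte Carlo error).

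**What to change.** In 8.3.3, define the primary estimate as the marginal risk difference in week-4 cure, AM minus PZQ. Take it from a logistic model with treatment, log(baseline egg count + 1) for Sm and for Sh, and preferably the species stratum used in randomisation. Standardise over all children in the analysis set and give a robust 95% interval. State the unit of each count, because adding 1 before the log depends on it.

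Keep the -10% margin and the three-way reading of the interval. Do not substitute the model's odds ratio, which cannot be read against a margin in percentage points. Report the crude Wilson-score difference as a sensitivity analysis.

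The cost is one paragraph in the protocol, mirrored in the SAP and fixed before any outcome analysis, with no new data. The small downside is that the primary estimate becomes model-based, although its target is unchanged.

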8.3.4. Secondary and tertiary analysis

Secondary analyses

The efficacy of the two treatments over time will be assessed both by calculating the two-sided 95% CI for the difference in proportions of cured subjects at different time points as well as using a mixed effects logistic regression model. Schistosomiasis infection at specific time points will be used as the outcome and treatment and visit as independent variables with a random intercept. Subsequent analyses of the cure rate per *Schistosoma* species and by *Schistosoma* infection intensity will be analyzed in a similar way including those characteristics as covariates in the model. The analyses for

ERR will be done using a linear mixed effects model with a random intercept and a logit link function separately for each *Schistosoma species*. All comparison of proportions will be done using the Chi-square or Fisher's exact test and comparison of continuous characteristics will be done using the Wilcoxon rank sum test. The sensitivity of a specific diagnostic test will be calculated as the proportion of children with schistosomiasis (based on the reference standard used) who have a positive result. The specificity of a diagnostic test will be calculated as the proportion of children without schistosomiasis who have a negative result. The positive predictive value of a diagnostic test will be calculated as the proportion of children with schistosomiasis with a positive result. The negative predictive value of a diagnostic test will be calculated as the proportion of people with a negative result who do not have schistosomiasis. These different values of both novel and classic diagnostic tests will be calculated together with 95% confidence intervals. Composite reference standards will be created by the investigators of the study and will be used as a comparison. An alternative reference standard will be calculated using latent class analysis methodology. The prevalence and patterns of resistant mutations between the two treatment groups will be compared using Chi-square or Fisher's exact test.

Safety analyses

All non-serious and serious adverse events will be grouped according to a pre-specified side-effect coding system and tabulated. The number of subjects experiencing any adverse event, any serious adverse event, and any drug-related serious adverse event up to 4 weeks after PZQ and AM administration will be compared between treatment groups using Fisher's exact test. Safety will be analyzed using the all-subjects-treated approach for each time point separately. The safety results during the other AM administration visits will be tabulated in a similar way, but no formal statistical comparison is planned.

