2.2. Secondary objectives

1. To evaluate the safety and cumulative efficacy of two additional courses of AM (at 6-week intervals each) for the treatment of schistosomiasis, compared to a single course of AM, and compared to the standard PZQ regimen (control arm).

Endpoint measures:

- Efficacy: CR, as assessed by microscopy, after the second and after the third AM administration (at week 10 and 16, 24 and 48 see study flowchart),
- Safety: Frequency and pattern of AEs and SAEs up to 4 weeks after the second and third AM administration.
- 2. To determine the egg reduction rate (ERR) obtained after single and repeated courses of AM compared to the standard PZQ regimen.
 - Endpoint measure: ERR after administration of PZQ and after each AM course (at week 4, 10, 16, 24 and 48 see study flowchart).
- 3. To determine the parasitological efficacy of single and repeated courses of AM by *Schistosoma* species and by infection intensity.

Endpoint measures: CR and ERR by initial *Schistosoma* infection intensity after PZQ administration and single and repeated courses of AM. (measured at week 4, 10 and 16 after first AM administration)

- 4. To assess the impact of repeated AM courses on schistosomiasis-related morbidity. Endpoint measures: Prevalence and severity of general and organ-specific schistosomiasis morbidity (as assessed by clinical evaluation, ultrasound, point-of-care morbidity markers and hemoglobin level) at week 24 and week 48 compared to baseline and compared to the control arm.
- To determine the diagnostic performance of novel schistosomiasis antigen- and DNA-based diagnostic assays to monitor antischistosomal treatment response.
 Endpoint measures: Sensitivity and specificity of the different conventional and novel diagnostic tests at baseline and at defined time points after treatment compared to conventional microscopy, and to composite reference standards.

6. To determine the effect of repeated AM courses on prevalence of *P. falciparum* infection as well as on incidence and morbidity of clinical malaria in school-age children with schistosomiasis.

Endpoint measures:

- Prevalence of malaria infection, as assessed by molecular testing of dried blood spots at baseline and week 24 and 48.
- Incidence of clinical malaria, as assessed by the number of incident malaria cases diagnosed through passive case detection during the study period (by standard malaria rapid tests and molecular diagnostics on dried blood spots).

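### The mixed cure model in 8.3.4 does not estimate the visit-, species- or intensity-specific treatment effects that the objectives name, and the only tests listed are unpaired although some questions are within-child

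*Protocol*

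**What the plan says.** Section 8.3.4 plans two analyses of cure over time. One is "calculating the two-sided 95% CI for the difference in proportions of cured subjects at different time points". The other is a mixed logistic model, described as: "Schistosomiasis infection at specific time points will be used as the outcome and treatment and visit as independent variables with a random intercept". No product of treatment and visit is mentioned.

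Cure by species and by infection intensity is to be handled similarly, "including those characteristics as covariates in the model". ERR is treated differently, with a "linear mixed effects model with a random intercept and a logit link function separately for each" species.

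For everything else, all comparisons of proportions go to chi-square or Fisher's exact test, and "comparison of continuous characteristics will be done using the Wilcoxon rank sum test". No paired method is named.

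The objectives in 2.2 ask for more than arm-versus-arm contrasts:

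- Objective 1 wants three AM courses "compared to a single course of AM, and compared to the standard PZQ regimen (control arm").
- Objective 3 wants efficacy by species and by infection intensity.
- Objective 4 wants morbidity "at week 24 and week 48 compared to baseline and compared to the control arm".

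Section 3 has two arms only: AM in three courses, and PZQ once. Section 8.1 hypothesises non-inferiority after one course and superiority after repeated courses. Section 4.3 says "superiority of repeated courses of AM to PZQ (cure rate of at least 85% after 3 courses) can also be demonstrated" with similar power.

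**The concern.** The design makes the treatment contrast change over time. At week 4 it is one AM course against PZQ. At week 16 it is three courses against the same single PZQ dose. A model with one treatment coefficient assumes the log odds ratio is the same at every visit, which contradicts the trial's own hypotheses. If AM is worse early and better late, the coefficient can sit near zero and describe neither visit.

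The same applies to objective 3. A main effect for species says that cure is more or less likely with one species. It does not say whether AM does better or worse against PZQ in that species.

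The third issue is pairing. There is no single-course arm, so three AM courses against one means the same children at week 16 and week 4. Morbidity against baseline is also within child. Chi-square, Fisher and rank sum tests assume independent samples.

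At stake is a published model summary that conflicts with the visit-specific intervals beside it, an objective 3 result for cure that comes only from adjustment, and lost power for the within-child questions.

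**Working it through.** **1. The plan's own sample size.** Inputs from 4.3 and 8.3.3: cure 75% in both arms, margin 10 points, two-sided 95% CI, 80% power.

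n per arm = 2 × 0.75 × 0.25 × (1.960 + 0.842)² / 0.10² ≈ 295, against 300 stated. The figure reproduces.

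Superiority, 85% against 75%, n = 300 per arm:
- SE under the null = √(2 × 0.80 × 0.20 / 300) = 0.0327
- SE under the alternative = √((0.85 × 0.15 + 0.75 × 0.25) / 300) = 0.0324
- power = Φ((0.10 − 1.96 × 0.0327) / 0.0324) ≈ 87%

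So the claim of similar power also holds.

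**2. One coefficient against visit-specific effects.** The curves are assumptions, except that 75% for PZQ and 85% after three AM courses come from 4.3 (65% is the AM threshold there).

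| Week | AM | PZQ | Odds ratio |
|---|---|---|---|
| 4 | 65% | 75% | 0.62 |
| 10 | 75% | 75% | 1.00 |
| 16 | 85% | 75% | 1.89 |
| 24 | 70% | 70% | 1.00 |
| 48 | 55% | 60% | 0.81 |

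The logistic fit with treatment and visit only (no random intercept) returns a single odds ratio of 0.95.

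Adding a random intercept (SD 1, assumed) does not change the picture:
- AM 75/80/85% against PZQ 75/75/75% at weeks 4/10/16: one odds ratio of 1.41. With the interaction: 1.02, 1.39 and 2.12.
- AM 60/75/85% against PZQ 75/72/70%: one odds ratio of 1.05. With the interaction: 0.44, 1.16 and 2.82.

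**3. What the other planned analysis shows.** Wilson-score intervals for the difference, on the table above with 300 per arm:
- week 4: −17.2 to −2.7 points
- week 16: +3.6 to +16.3 points

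The per-visit intervals therefore show the reversal that the model averages away. With true rates of 85% and 75%, the lower limit at week 16 exceeds zero in 87% of simulations.

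**4. Species as a covariate.** Assumed cure, AM against PZQ: *S. haematobium* 80% against 75% (odds ratio 1.33), *S. mansoni* 60% against 75% (odds ratio 0.50). With species as a covariate only, the model gives one odds ratio of 0.78.

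**5. Unpaired tests on paired data.** n = 300 children measured twice; r is the within-child correlation (assumed, since the protocol gives none).

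With cure 75% at both times, chi-square uses SE = √(2pq/n), but the true SE is √(2pq(1 − r)/n). So type I error = 2 × [1 − Φ(1.96 / √(1 − r))]. At r = 0.4 this is 2 × [1 − Φ(2.53)] ≈ 1.1%.

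For a true change from 75% to 82% at r = 0.4:
- chi-square SE = √(2 × 0.785 × 0.215 / 300) = 0.0335
- true SE = √((0.1875 + 0.1476 − 2 × 0.4 × √(0.1875 × 0.1476)) / 300) = 0.0259
- chi-square power = Φ((0.07 − 1.96 × 0.0335) / 0.0259) ≈ 56%
- McNemar power = Φ(0.07 / 0.0259 − 1.96) ≈ 77%

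Simulation over a range of r:

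| r | Chi-square type I | Chi-square power | McNemar power |
|---|---|---|---|
| 0 | 4.9% | 55% | 55% |
| 0.2 | 2.8% | 56% | 65% |
| 0.4 | 1.1% | 56% | 77% |
| 0.6 | 0.2% | 58% | 92% |

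McNemar's type I error stays at about 5% throughout.

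**The case against.** The strongest reply is that the plan already contains the visit-specific analysis. The sentence just before the model description commits to a confidence interval for the difference at each time point, and step 3 shows that it does the job. A reader might infer that the repeated-course objective cannot be answered, or that superiority has no test. Neither is supported: the interval is the test, with superiority meaning a lower limit above zero.

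On objective 3, ERR is half of the endpoint and is modelled separately by species. Section 8.3.5 calls the secondary-objective analyses subgroup analyses, and handling cure similarly could include intervals within strata. So it would be wrong to say that objective 3 gets no answer. What stands is that the one method spelled out for cure by species and intensity, covariates in the model, does not produce that answer.

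On pairing, a reader might fear false positives. The error runs the other way: under positive correlation the unpaired tests are conservative and cost power. They are also suitable for the arm comparisons in objective 4, and the random intercept does handle within-child correlation in the cure model. Its visit effect is shared by both arms, however, so without an interaction it does not isolate the change in the AM arm from week 4 to week 16.

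A reader might also count weeks 10, 16, 24 and 48 as four superiority claims, with a chance of at least one false claim of 1 − 0.975⁴ = 9.6% if independent, or 6.5% at correlation 0.7. Nothing in the protocol declares four claims, and 4.3 ties superiority to the state after three courses.

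Finally, the SAP could add terms and paired tests. That is true, but it would then depart from a model and a list of tests that the protocol states explicitly.

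**Conclusion.** The point holds as a mismatch between the stated methods and the named contrasts. It is not a failure to address the objectives.

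- The cure model as written yields one treatment effect over visits and none by species or intensity. How misleading this is depends on the true curves. In the assumed examples it turns 0.62 to 1.89 into 0.95, and 1.33 and 0.50 into 0.78.
- The unpaired tests, read literally, cost up to about a third of the achievable power for the within-child questions in the example. The loss depends on the correlation, is nil at r = 0, and does not raise the false-positive rate.
- The superiority visit is implied but not stated. This is an ambiguity to close, not evidence of an inflated error rate.

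All of this concerns secondary analyses. The week-4 non-inferiority test in 8.3.3 is unaffected. Severity: should-fix.

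**What to change.** Amend 8.3.4, and carry the same wording into the SAP:

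1. Add treatment × visit to the mixed cure model and report the treatment contrast at each visit.
2. For cure by species and intensity, add treatment × species and treatment × intensity, or report stratum-specific differences with intervals.
3. Limit chi-square, Fisher and rank sum tests to comparisons between arms. For changes from baseline and for three against one AM course, use within-child contrasts from the mixed model, McNemar's test or the signed-rank test. Label three against one course a before-after comparison, because there is no single-course arm and anything else that changes between weeks 4 and 16 moves with it.
4. State that the superiority hypothesis is judged at week 16, after three courses, with the other visits supportive.

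The cost is wording and a few more model parameters; stratum-specific intervals will be wider than the pooled one. No new data, visits or participants are needed, and the superiority claim would rest on one visit.
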